## **9. RESPONSE EVALUATIONS AND MEASUREMENTS**

### **9.1 Progression-free Survival**

Progression-free survival is defined as the time from Day 0 of BMT until the date of objective radiological PD according to RECIL or death (by any cause in the absence of PD). Patients who are alive and free from PD will be censored at the date of last tumor assessment. Patients who begin subsequent therapy prior to PD or death will be censored at the date of last tumor assessment prior to the start of subsequent therapy.

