### **10.4 Data Analysis**

Descriptive statistics, including mean, median, standard deviation, and range for all continuous measures, will be tabulated and reported. Percentages and frequencies for all categorical measures will also be presented. Time-to-event endpoints will be reported using Kaplan-Meier estimates, with 95% CIs for median time to event. A full description of the analysis will be included in the Statistical Analysis Plan.

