#### **10.4.2 Efficacy Analysis**

All efficacy analyses will be performed using the Efficacy Analysis Set.

- PFS is defined as the time from Day 0 of BMT to objective radiological PD or death on study. PFS will be evaluated as Kaplan-Meier estimates of the percentage of subjects who receive at least one dose of study drug and who are alive and free of PD or relapse at 2 years post-BMT according to RECIL (Younes et al 2017). Data for subjects who are still alive and free from progression at the time of data cut-off date, are lost to follow-up, have discontinued the study, or have initiated a subsequent protocol therapy will be censored on last assessment (or, if no post-baseline tumor assessment, at the time of first dose plus 1 day). Approximate 95% CI for median duration of PFS will be computed using the formula proposed by Brookmeyer and Crowley.
- Minimal residual disease status will be examined by NGS on all bone marrow aspirate and blood samples collected up to 2 years post-BMT to determine the conversion rate from MRD+ to MRD while taking acalabrutinib, correlate MRD status with PFS, and identify mutations that correlate with disease relapse. An MRD status will be defined as all results from whole blood and BM that are negative for the presence of residual clonal cells (with assay sensitivity of 10^-6). An MRD+ status will be defined as all results from whole blood or BM that are positive for residual clonal cells per Adaptive Biotechnologies' reporting methods.

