| AE evaluationst                 |           |                       | X   | X            | X  | X   | X   | X                                   |                        |
| PFS follow-up                              |           |                       |   |              |  |   |   |                                     | X                      |

- a. Acalabrutinib maintenance therapy begins on Day 100 post-BMT
- b. Post-BMT screening should occur between Day +80 and Day +100
- c. Begin between Day +100 and Day +120
- d. Clinic visits will be monthly on Day 1 for Cycles 2-6 only (See Planned Clinic Visits table below)
- e. Cycles 7-12 only: clinic visits will **occur every 2 months for 6 months** (See Planned Clinic Visits table below)
- f. Cycle 13 and beyond until 5 years post-BMT: **clinic visits will occur every 3 months** (See Planned Clinic Visits table below)
- g. Within 30 days of last dose of acalabrutinib
- h. A telephone call to assess PFS every 3 months can be made in lieu of an office visit
- i. Blood pressure, pulse, oxygen saturation, and temperature
- j. Subjects should be in supine position and resting for at least 10 minutes before any study-related ECGs are taken.
- k. For women of childbearing potential only at the time of screening (post- and prior to BMT) and 72 hours before the start of treatment. Urine or serum pregnancy tests are acceptable.
- l. Patients with a known history of human immunodeficiency virus (HIV) or who are HIV antibody positive should be tested for HIV RNA during screening. No further testing beyond screening is necessary if PCR results are negative, except if clinically indicated (see Section 6.5.6).
- m. Only patients who are anti-HBc positive, or have a known history of HBV, should have quantitative PCR testing for HBV DNA performed during screening and every 3 months thereafter. Monitoring (every 3 months) should continue until 12 months after last dose of acalabrutinib. As IVIG may cause false positive hepatitis serology, monthly PCR testing is not required in patients who are currently receiving or received prophylactic IVIG within 3 months before study enrollment and have a documented negative anti-HBc test before the initiation of IVIG therapy (see Section 6.5.6).

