- n. Patients with a known history of hepatitis C virus (HCV) or who are hepatitis C antibody positive should be tested for HCV RNA during screening. No further testing beyond screening is necessary if PCR results are negative, except if clinically indicated (see Section 6.5.6).
- o. If not obtained during Screening #1 (prior to BMT)
- p. Collect a fresh lymphoma biopsy at disease progression
- q. **MRD analysis with blood sample:** Collect a blood sample prior to beginning maintenance on Day +100 (Screening #2), 6 months (~Cycle 4 Day 1), 1 year (~Cycle 10 Day 1) and 2 years post-BMT (~Cycle 22 Day 1).
- r. **MRD analysis with bone marrow biopsy and aspirate:** Collect a bone marrow biopsy and aspirate prior to beginning maintenance on Day +100 (Screening #2) and at 1 year post-BMT (~Cycle 10 Day 1).
- s. CT/MRI/FDG-PET scans will be done post-BMT (Day 80-100), at 6 months, 12 months, 18 months and 24 months. Thereafter, scans will be done per institutional standard operating procedures.
- t. Record all AEs regardless of seriousness or relationship spanning from the first dose of acalabrutinib until 30 calendar days after discontinuation or completion of study drug.
- u. Coagulation testing will include PT/INR or aPTT.

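### PFS censoring depends on the last scan, but no scan interval is set after month 24: late PFS and the median can be biased if scans are symptom-driven, and the month-24 scan can fall before the 2-year time point (minor)

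*Combined protocol and SAP*

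**What the plan says.** - **Censoring rule.** Section 9.1 counts radiological progression by RECIL, or death, from Day 0 of BMT. For patients without an event: "Patients who are alive and free from PD will be censored at the date of last tumor assessment". Those who start other treatment first "will be censored at the date of last tumor assessment prior to the start of subsequent therapy". Section 6.5.14 describes tumor assessments as imaging.
- **Second statement of the rule.** Section 10.4.2 says that patients who are event-free at cut-off, lost, off study, or on later therapy "will be censored on last assessment (or, if no post-baseline tumor assessment, at the time of first dose plus 1 day". For later therapy the wording is "have initiated a subsequent protocol therapy will be censored on last assessment", without the time limit in 9.1.
- **Scans.** Appendix D, footnote s, fixes scans at Day 80-100 and at 6, 12, 18 and 24 months. Then: "Thereafter, scans will be done per institutional standard operating procedures".
- **Follow-up to year 5.** Section 6.4.6 sets 3-monthly follow-up and lists only a biopsy at progression and PFS status. Footnote h adds: "A telephone call to assess PFS every 3 months can be made in lieu of an office visit".
- **Outputs.** Section 10.4: "Time-to-event endpoints will be reported using Kaplan-Meier estimates, with 95% CIs for median time to event". Section 10.4.2 names the 2-year Kaplan-Meier percentage and adds: "Approximate 95% CI for median duration of PFS will be computed". The final analysis follows the last patient's last visit (10.5.1), so data from years 2 to 5 enter the curve.
- **Month-24 scan.** The Planned Clinic Visits table puts it at Cycle 22 Day 1. Section 6.4.4 and footnote s put it at 24 months post-BMT.

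**The concern.** After month 24, events and event-free time may be observed by different routes. A death counts whenever it occurs, and a progression suspected at a visit or call is likely to lead to a scan and then counts. A patient who stays well is credited only up to the last scan, and the protocol sets no interval for further scans. If scans are partly prompted by symptoms, being censored soon after month 24 is a marker of staying well. That is informative censoring. It lowers the late curve and can make a median appear that the data do not support.

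Two smaller matters go with this. The two statements of the rule are not identical. And a scan labelled 24 months that is taken before Day 730 removes event-free patients with no later scan just before the primary time point.

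**Working it through.** **1. The plan's own figure.** Section 10.2 uses 45 patients and an observed 80%. The exact 95% interval for 36/45 is 65.4% to 90.4%, which reproduces its 65%-90%. The 80% at 24 months is the planning value used below.

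**2. Late PFS: inputs.** Assumed, because the documents give none of these: constant hazard from Day 0; a share *q* of patients re-scanned every 6 months after month 24; the rest scanned only on suspicion, so that a share *s* of their progressions is found; no loss to follow-up.

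- True 60-month PFS: S60 = 0.80^(60/24) = 0.572.
- True median: 24 × ln 2 / (−ln 0.80) = 74.6 months, beyond the 60-month follow-up.

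**3. Late PFS: formulas (large sample).** Let a = q + (1 − q)s, the share of progressions found, and b = (1 − q)s × S60 / a.

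- Censoring at last scan: KM(60) = 0.80 × (S60 − b) / (0.80 − b).
- Censoring at last PFS contact: KM(60) = 0.80 − a × (0.80 − S60).

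Example, q = 0.5 and s = 1: a = 1 and b = 0.286. Last scan gives 0.80 × 0.286 / 0.514 = 0.45. Last contact gives 0.57.

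| q | s | Last scan | Last contact | Median reached by month 60 (scan / contact) |
|---|---|---|---|---|
| 100% | any | 57% | 57% | 16-17% / 16-17% |
| 75% | 100% | 52% | 57% | 40% / 17% |
| 75% | 50% | 55% | 60% | 27% / 8% |
| 75% | 0 | 57% | 63% | 20% / 4% |
| 50% | 100% | 45% | 57% | 72% / 17% |
| 50% | 50% | 50% | 63% | 48% / 4% |
| 50% | 0 | 57% | 69% | 22% / 0% |

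The last column comes from simulation with 45 patients per trial. The simulated 60-month estimates agree with the formulas to within about 1 point. The rows with s = 0 matter: re-scanning is incomplete there, yet last-scan censoring is unbiased and contact-based censoring is too high.

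**4. Late PFS: other assumptions.** A second simulation took constant hazard from Day 100, 80% at 2 years, true 5-year PFS 54%, 6-monthly re-scans, all progressions found, and detection lags of 0 to 365 days.

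- 5-year estimate: 54-56% with all re-scanned, 52-54% with 90%, 49-51% with 75%, 40-45% with half.
- 3-year estimate (truth 70%), half re-scanned: 64-65% at lags of 0-30 days but 72-73% at 365 days. Late detection can reverse the direction at 3 years.
- If instead every patient is due 6-monthly scans and misses half of them at random (lag 90 days), the 5-year estimate is 52%.

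**5. Month-24 scan.** Cycle 22 Day 1 = start day + 21 × 28 = start day + 588. The start windows are Day 100 ± 7 (synopsis) and Day 100 to 120 (Appendix D, footnote c). Two years is taken as Day 730.

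| Start day | Cycle 22 Day 1 | Days before Day 730 |
|---|---|---|
| 93 | 681 | 49 |
| 100 | 688 | 42 |
| 107 | 695 | 35 |
| 120 | 708 | 22 |

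Number at risk at Day 730 in the model of step 4, with the scan at Day 688 and half re-scanned:

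- Re-scanned: 22.5 × 0.80 = 18.0.
- Not re-scanned but with a later event by year 5: 22.5 × (0.80 − 0.543) = 5.8.
- Total: about 24 of 45.

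If the scan is assigned to Day 730, everyone without progression at the 18-month scan (Day 548) is still at risk: 45 × 0.853 = about 38. Across 50-100% re-scanned, the 2-year estimate was 79-83% (truth 80%), and 80-81% once the scan was assigned to Day 730.

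**The case against.** - **A reader might infer that incomplete re-scanning is enough to make the censoring informative.** It is not. The rows with s = 0 show no bias in the scan-based estimate. Scanning has to depend on symptoms or outcome. The design permits this but does not establish it.
- **A reader might infer that scanning stops at month 24.** Footnote s says that scans continue under institutional procedures. The largest effects need half the patients never to be routinely scanned again, with every progression found. Scans missed at random cost only about 2 points at 5 years.
- **A reader might infer that 9.1 and 10.4.2 contradict each other.** The parenthesis in 10.4.2 mentions tumor assessment and so points to the same rule. Only the less natural reading, counting a telephone contact, moves a patient's censoring date by up to about 3 years. Section 6.4.6 also ends long-term follow-up when other anticancer therapy starts, so the missing time limit has little effect after year 2.
- **The affected outputs are secondary.** No 3-, 4- or 5-year rate is a named output. Section 10.4 defers the full analysis description to the SAP, and no separate SAP text was available to check, so the absence of a sensitivity analysis is not shown.
- **Follow-up is more than a call.** Footnote f gives 3-monthly clinic visits to year 5, and 6.5.2 requires an examination at long-term follow-up. Examinations help to find progression, but they do not move the scan-based censoring date of a patient who is well.
- **Cycle labels are approximate.** Section 6.5.13 equates 2 years with about Cycle 22 Day 1 for MRD sampling. That explains the label, but censoring uses the actual scan date.

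These points limit the size of the concern. The unset interval, the differing wording and the early month-24 scan remain.

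**Conclusion.** The concern holds in a limited form, and its severity is minor. If scans after month 24 are partly symptom-driven, the Kaplan-Meier curve beyond 2 years and the median are biased downward, although long detection lags can offset or reverse this at 3 years. If re-scanning is near complete or unrelated to disease, the bias is small. The size cannot be fixed from the documents: with 75% re-scanned, the 5-year loss was 0 to 5 points in the model of steps 2 and 3, and with half it was 0 to 13 points (57% to 45% after rounding, 0.572 to 0.446 before). At the planned 80%, the true median lies beyond follow-up in these models, so the main effect is a median that appears when it should not.

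A reader might take this as undermining the primary result. The documents do not support that. Scans are fixed through month 24, the 2-year estimate moved by about 1 to 3 points, and no test or decision rule rests on it. What the early scan costs is mainly the number at risk at 2 years. All magnitudes rest on constant hazard and on the assumed re-scanning and detection.

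**What to change.** 1. State one rule in 9.1 and 10.4.2: the 9.1 rule of censoring at the last tumor assessment, including the limit to assessments before subsequent therapy starts.
2. Reconcile Cycle 22 Day 1 in the visit table with 24 months post-BMT in 6.4.4 and footnote s. For the 2-year estimate, assign scans within a defined window to nominal month 24.
3. For the median and PFS beyond month 24, add one sensitivity analysis that censors at the last documented progression-free status (scan, visit or contact). Report numbers at risk and the share of patients scanned after month 24. Present the two analyses as differently biased: scan-based is low if scanning is symptom-driven, contact-based is high if silent progression is missed. Do not make interpretation depend on an agreement threshold, because agreement does not exclude late detection.

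The cost is wording in two sections, the visit table and the SAP, plus one extra analysis. No extra patients or procedures are needed. The downside is a less firm statement about late PFS.

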## 5. STUDY DESIGN

This is a single arm, multi-center, Phase II study of subjects with MCL who will receive acalabrutinib as maintenance therapy post-BMT. In general, subjects will provide informed consent prior to BMT to collect the required central labs. However, a limited number of subjects may be allowed to provide informed consent following BMT, determined on a case-by-case basis by the Principal Investigator (PI). In this event, any of the study assessments required prior to BMT not performed for standard of care will not be required.

Subjects will undergo a standard of care BMT with conditioning regimen determined by the treating physician per institutional guidelines. The BMT is not considered part of this study. Following completion of the BMT, a second screening will begin between Day 80 and Day 100. Maintenance therapy with acalabrutinib will begin on Day 100 in 28-day cycles. Subjects will self-administer 129 mg acalabrutinib BID until they reach 2 years post-BMT (approximately 22 cycles). Subjects who experience PD while on study will be encouraged to provide a fresh biopsy to assess lymphoma genome alterations. All subjects will be followed for up to 5 years post-BMT for PFS.

Approximately 50 subjects are planned to be enrolled after receiving BMT.

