### **6.4 Study Assessment Timing**

The maintenance treatment period begins on the day the patient receives the first administration of acalabrutinib (Day 100). Dates for study visits and assessments will be determined based upon the first day after the BMT and should occur based on the timing parameters outlined in this protocol.

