#### **6.4.4 Cycle 13 and Beyond, Day 1 ( $\geq 16$ months post-BMT)**

- Physical examination and vital signs (including weight)
- ECOG performance status
- CBC and clinical chemistry panel
- Screening for viruses (see Section 6.5.6)
- Blood sample collection for MRD analysis

- CT/MRI/PET scans (18 and 24 months post-BMT)
- Treatment with acalabrutinib 129 mg PO BID
- Concomitant medication review and AE monitoring

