## Planned Clinic Visits

| Cycle 1  |           | d. Cycles 2-6 only:
clinic visits will occur every month |          |                                    |          |          |             | e. Cycles 7-12 only:
clinic visits will occur every 2 months |             |                                     |             |           |                                  | f. Cycle 13 and beyond until 5 years post-BMT:
clinic visits will occur every 3 months |             |                                     |             |             |           |             |             |                                     |  |
|----------|-----------|---|----------|------------------------------------|----------|----------|-------------|---|-------------|-------------------------------------|-------------|-----------|----------------------------------|---|-------------|-------------------------------------|-------------|-------------|-----------|-------------|-------------|-------------------------------------|--|
| C1
D1 | C1
D15 | C2
D1  | C3
D1 | C4
D1                           | C5
D1 | C6
D1 | C7
D1    | C8
D1  | C9
D1    | C10
D1                           | C11
D1   | C12
D1 | C13
D1                        | C14
D1   | C15
D1   | C16
D1                           | C17
D1   | C18
D1   | C19
D1 | C20
D1   | C21
D1   | C22
D1                           |  |
| Visit    | Visit     | Visit   | Visit    | Required
for
6 mo
imaging | Visit    | Visit    | No
Visit | Begin
every
2 mo
visits                                | No
Visit | Required
for
12 mo
imaging | No
Visit | Visit     | Begin
every
3 mo
visits | No
Visit   | No
Visit | Required
for
18 mo
imaging | No
Visit | No
Visit | Visit     | No
Visit | No
Visit | Required
For
24 mo
imaging |  |

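### The 24-month scan has two dates in the protocol; if it is done at Cycle 22 Day 1, the censoring rule in section 9.1 can distort the 2-year PFS estimate when few patients are scanned again

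*Combined protocol and SAP*

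**What the plan says.** Section 9.1 measures PFS from Day 0 of BMT and states: "Patients who are alive and free from PD will be censored at the date of last tumor assessment". Section 10.4.2 estimates the 2-year percentage by Kaplan-Meier and censors at the last assessment, omitting the word tumor.

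The scan date appears in three places. In the Planned Clinic Visits table, the Cycle 22 Day 1 column reads "Required For 24 mo imaging". Section 6.4.4 lists "CT/MRI/PET scans (18 and 24 months post-BMT)". Appendix D footnote s also says 24 months, then adds: "Thereafter, scans will be done per institutional standard operating procedures". None gives a window in days. Section 6.4 adds a general rule: "Dates for study visits and assessments will be determined based upon the first day after the BMT".

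The start day also varies. Section 5 says "Maintenance therapy with acalabrutinib will begin on Day 100 in 28-day cycles", the synopsis allows Day 100 plus or minus 7 days, and Appendix D footnote c says "Begin between Day +100 and Day +120".

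After 2 years, section 6.4.6 lists only a biopsy at progression and PFS status at each follow-up visit. Footnote h allows a telephone call instead of an office visit. Section 10.5.1 places the final analysis after the last visit of the last patient.

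**The concern.** If the scan is done when the visit table says, the last protocol-dated look at the tumor comes 22 to 49 days before the landmark. A patient who is clean on that scan and not scanned again is censored on that date.

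Patients start on different days, so their Cycle 22 Day 1 dates differ too. Progression found on a late Cycle 22 Day 1 scan, or a death before Day 730, is then divided by a risk set already reduced by patients scanned clean a few days earlier. Each such event takes too large a step off the curve. The accuracy of the primary estimate would depend on scans that the protocol does not schedule.

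**Working it through.** **The plan's own figure.** Section 10.2 gives a 95% CI of 65%–90% for 80% observed in 45 patients. The exact (Clopper-Pearson) interval for 36/45 is 65.4%–90.4%, so the figure reproduces, but it treats all 45 outcomes at 2 years as known.

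**Scan day.** Cycle 22 Day 1 = start day + 21 × 28 = start day + 588.

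| Start day | Cycle 22 Day 1 | Days before Day 730 |
|---|---|---|
| 93 | 681 | 49 |
| 100 | 688 | 42 |
| 107 | 695 | 35 |
| 120 | 708 | 22 |

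**How one event acts on a depleted risk set.** Suppose the curve stands at 0.80 with 36 of 45 patients event-free, and one more event occurs before Day 730. The estimate becomes 0.80 × (n − 1)/n, where n is the number still at risk:
- n = 36: 0.80 × 35/36 = 0.778
- n = 18: 0.80 × 17/18 = 0.756
- n = 9: 0.80 × 8/9 = 0.711
- n = 4: 0.80 × 3/4 = 0.60

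**Size of the gap itself.** Assume no events before Day 100 and a constant hazard after it of −ln(0.80)/630 per day, so that true PFS at Day 730 is 80%. True PFS is then 81.4%, 81.2%, 81.0% and 80.6% on Days 681, 688, 695 and 708. Between 0.8% and 1.7% of those still event-free have an event in the gap. Stopping early is therefore worth only about 1 point; the larger effect comes from the staggered dates.

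**Simulation.** Inputs: 45 patients; the hazard above; scans at Day 1 of Cycles 4, 10, 16 and 22; progression dated at the scan that finds it; deaths at their own date; later scans, if any, every 6 months to 5 years; Kaplan-Meier read at Day 730. Starts are spread over Day 93–107, 100–120 or 93–120, and results are ranges over the three. The share scanned later and the share of events that are deaths are assumptions.

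| Scanned again | All events progression: mean | A quarter deaths: mean | At risk at Day 730 (no deaths / quarter deaths) |
|---|---|---|---|
| 0% | 70–72% (SD 14–18) | 74% (SD 12–13) | 0 / 3 |
| 25% | 77–78% (SD 8) | 78% (SD 7) | 9 / 11 |
| 50% | 79–80% (SD 6–7) | 79–80% (SD 6–7) | 18 / 20 |
| 100% | 81% (SD 6) | 81% (SD 6) | 36 / 36 |

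The share of runs missing the truth by more than 10 points is about 34–41% at 0% scanned again, 16–21% at 25%, 11–14% at 50% and 9–10% at 100%.

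**Is the stagger the cause?** With every start on Day 100 and no later scans, the mean is 81% (SD 6) without deaths and 78% (SD 12) with a quarter deaths. Without deaths, nobody is at risk at Day 730 and the mean is still close to the truth. A low number at risk does not by itself explain the drop.

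**Calendar reading.** With the scan on Day 723–737 and no later scans, the mean is 81–82% (SD 6), with about 20 at risk.

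**The case against.** The strongest reply is that the documents point to the calendar date. Section 6.4 times assessments from the BMT, section 6.4.4 and footnote s say 24 months, and the visit table is a planning grid that gives no day count. This favours the calendar reading, on which little is lost. It does not remove the conflict: section 6.4 does not itself place a scan at 24 months, and the table names Cycle 22 Day 1 as the visit required for that imaging.

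The second reply is that the large figures need almost nobody to be scanned again. Footnote s expects institutional scans, footnote f has clinic visits for "Cycle 13 and beyond until 5 years post-BMT", and the analysis waits for the last visit. This also stands. At half or more scanned again, the bias is within about 1 point.

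Third, if the telephone contacts counted as the last assessment in section 10.4.2, patients would stay at risk past Day 730. The parenthesis there about having no post-baseline tumor assessment, together with section 9.1, points the other way, but the two wordings should be aligned. Section 10.4 also defers detail to a Statistical Analysis Plan whose text was not available here, and a visit-window rule may be there.

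A reader might infer that the primary estimate will be about 10 points too low, or is invalid because nobody is at risk at 2 years. The documents do not support this: they do not give the share scanned again, and the visit-table reading is one of two. Nor does the approximate Cycle 22 Day 1 wording in section 6.5.13 and footnote q settle the matter, since it concerns the MRD blood sample and not imaging.

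**Conclusion.** The scan date is inconsistent, and on one of its two readings the stated censoring rule can give a wrong primary estimate. The shortfall is about 6 to 10 points if nobody is scanned after Cycle 22 Day 1 and 2 to 3 points at a quarter; at half or more the estimate is within about 1 point of the truth. On the calendar reading it is at most about 2 points, upward.

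These sizes rest on an assumed true 2-year PFS of 80%, a constant hazard after Day 100, staggered starts and no other dropout. The arithmetic on scan days is certain; how much it matters depends on later scanning, which the documents leave open. It should be fixed, because the repair is cheap and removes that dependence.

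**What to change.** 1. Use the term last tumor assessment in both 9.1 and 10.4.2. For the 2-year estimate, assign planned scans to their nominal 6, 12, 18 and 24 months. A clean 24-month scan then counts as event-free at Day 730, and progression on it as an event at Day 730. Keep actual dates for deaths and for progression on unscheduled scans. Read the Kaplan-Meier estimate at Day 730, not at the end of the scan window.
2. Reconcile the imaging entry in the Planned Clinic Visits table with section 6.4.4 and footnote s by stating the 24-month scan window in days post-BMT.

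Adopt part 2 only together with part 1. A scan on Day 730–744 dated as performed would leave progression found after Day 730 out of the 2-year estimate and give about 84–85%.

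Leave the MRD blood-draw wording in 6.5.13 and footnote q unchanged. Moving that draw past Day 730 could put it after treatment ends, while conversion is defined on treatment.

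With the fix and no later scans, the simulated mean is 80% (SD 6) for a Day 730–744 scan and 81% (SD 6) if the scan stays at Cycle 22 Day 1. The cost is wording only, with no added scans. In the first case the scan moves 22 to 49 days later and the estimate is about 1 point less favourable than with full later scanning. In the second, 22 to 49 unobserved days are credited as event-free, about 1 point upward. Either way, 2-year PFS uses nominal rather than actual dates for planned scans.
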